11.3 Statistical Analysis Plan

All patients who receive any dose of the study agent will be included in the analysis for efficacy and safety. We will follow standard reporting guidelines for adverse events, and summarize safety data by category, severity and frequency. For the primary efficacy analysis, we will estimate the CRc rate for the combination treatment, along with the 95% credible interval. Patients who drop out of the study before completing all the cycles will be treated as “failures” for the primary analysis.

Patients’ demographic and clinical characteristics will be summarized using descriptive statistics. Specifically, categorical covariates will be summarized by frequencies and percentages and their associations with responses will be assessed using Fisher’s exact test or its generalization. Continuous covariates will be summarized by means, standard deviations, medians and ranges, and the difference between responses groups will be assessed using the Wilcoxon rank sum test. Paired t-tests or Wilcoxon signed-rank tests will be used to determine the immunological and molecular changes in the peripheral blood and bone marrow from baseline to the time of response, and to the time of disease progression.

We will estimate the rates of partial response and bone marrow blast reduction $\geq 50\%$ within 3 months, along with 95% confidence intervals. For each subject, duration of response (DOR), event-free survival time and overall survival time will be calculated. DOR is defined as the time period from the first documentation of CRc to disease

recurrence, disease progression, or death whichever occurs first. Event-free survival time is defined as the time period from the date of treatment initiation to the date of documented treatment failure, relapses from CRc, or death from any cause, whichever occurs first. The observed DOR/EFS will be censored at the last follow-up if the patient is alive and no events observed. The overall survival time is defined as the time duration from treatment start till death or last follow-up if the patient is alive. The distributions of time-to-event endpoints including OS and DOR will be estimated using the Kaplan-Meier method. Comparisons of time-to-event endpoints by important covariate subgroups will be made using the log-rank tests. Progressive disease will be determined using ELN (2017) recommendations and is defined as any one or more of the following:

- 50% increase in marrow blasts over baseline (a minimum 15% point increase is required in cases with < 30% blasts at baseline; or persistent marrow blast percentage of > 70% over at least 3 months; without at least a 100% improvement in ANC to an absolute level ($> 0.5 \times 10^9/L$ [500/mL], and/or platelet count to $> 50 \times 10^9/L$ [50 000/mL] non-transfused);
- 50% increase in peripheral blasts (WBC \times % blasts) to $> 25 \times 10^9/L$ ($> 25 000/\mu L$);
- New extramedullary disease

The Investigator is responsible for completing Safety/Efficacy summary reports and submitting them to the IND office Medical Monitor for review, as follows:

Phase Ib Portion:

Submit a Toxicity Summary after the first six evaluable patients complete the first 28 days of study treatment, and every 6 patients thereafter, and before any dose modification or dose expansion.

Phase 2 Portion:

Submit an Efficacy/Toxicity Summary after the first five evaluable patients, per cohort, complete the first 28 days of study treatment and every 5 evaluable patients per cohort, thereafter. On every report submission, the information from previous reported patients will need to be updated to include toxicity assessment by the end of the first 28 days of treatment, and efficacy assessment by the end of cycle 3.

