7.2 Evaluation During Treatment

- 7.2.1 During Cycle 1 Day 7-12 patients will be admitted to the inpatient service and have labs done at least daily to monitor closely for TLS, proliferative disease, and electrolyte changes. Patient can be treated as an outpatient if WBC $< 10,000$ with approval from the PI.

- 7.2.2 Physical exam on day 1 of each cycle (± 1 days) for the first 4 cycles.
- 7.2.3 CBC, platelet count, hemoglobin, differential at least twice weekly for the first 3 cycles, then at least once a week (differential can be omitted if WBC is $\leq 0.5 \times 10^9/L$). Outside labs may be used, but the PI/Treating physician must review all protocol specific outside lab results and determine the clinical significance of abnormal values then sign/date the results or dictate this process in the medical record.
- 7.2.4 Creatinine, total bilirubin, ALT, K, Mg, Ca, sodium, chloride, and CO₂ (HCO₃) on day 1 prior to start of quizartinib, at least twice weekly for the first 3 cycles, then at least once a week. For initial labs and initial management of electrolyte imbalances and prevention of tumor lysis syndrome patients will be admitted and monitored inpatient for cycle 1 Days 7-12 (section 5.5.4).
- 7.2.5 Laboratory tests can be ordered more frequently if mandated by development of peripheral blast/blood counts or electrolyte/liver function test abnormalities.
- 7.2.6 Bone marrow aspiration for differential and PCR for FLT3 on day 28 (± 7 days) of cycle 1, day 28 of cycle 3 (± 7 days), then every 2 cycles. Bone marrow tests can be ordered more frequently if mandated by development of peripheral blood counts. No repeat bone marrow is necessary if nonresponse or progressive disease can be unequivocally diagnosed from peripheral blood tests or, in patients with a WBC < 0.3 if the bone marrow test is considered noncontributory by the investigator at any time point.
- 7.2.7 Concomitant medication data will not be collected or entered into the case report form (Prometheus is the case report form for this study). Concomitant medication data will not be collected or entered into the case report form except for concomitant hydroxyurea if administered during the first cycle; however, the subject's medication record will contain a list of concomitant medications.

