8.0 CRITERIA FOR RESPONSE

Response criteria will be modified from the International Working Group for AML(52). Responders are patients who obtain a Composite Complete Remission Rate (CRc) with or without cytogenetic response, hematologic improvements, and morphologic leukemia-free state. CRc rate is defined as the confirmed remission rate of all complete and incomplete CRs (i.e., CR+ CRp + CRi).

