8.8 Best Response measurement

Response will be measured and defined for primary endpoints as the best response achieved during the first 3 cycles of therapy, or at time off study, for those patients discontinuing treatment before the completion of 3 cycles of therapy. Best response is defined to be the best-measured response (CRc=CR+CRp+CRi, PR, or marrow clearance) post-treatment up to that time. Best response will also be evaluated for the full treatment period using all assessments up to and including treatment discontinuation.

9.0 DISCONTINUATION OF TREATMENT:

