9.1 Discontinuation Criteria for Individual Patients

9.1.1 Patient Withdrawal

Patients may voluntarily withdraw consent to participate in the clinical study at any time and without giving any reason. Their withdrawal will not jeopardize their relationship with their healthcare providers or affect their future care. Patients may also choose to withdraw from study treatment, but agree to remain in the study for follow-up procedures.

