9.1.4 Follow-Up at Treatment Discontinuation or Early Withdrawal

Patients who discontinue treatment for any reason should complete end-of-treatment procedures when possible. End of treatment procedures will include a physical examination, CBC with differential and platelets and a limited chemistry profile (total bilirubin, serum creatinine, SGPT or SGOT). A bone marrow aspiration may be recommended only if non-response or progressive disease cannot be unequivocally diagnosed from peripheral blood. Although treatment will be discontinued at that time, all patients who do not withdraw consent for follow-up, die, or become lost to follow-up, will remain on study for follow-up evaluations. Subject will be followed for toxicity for at least 30 days after the last protocol treatment. The 30-day (+/-7 days) follow-up visit will be scheduled as a clinic visits for clinical evaluation and physical examinations. If the patient cannot make it to the MDACC clinic for this visit, the required follow up treatment procedures may be done with a local physician and the records forwarded to MDACC. The research nurse will contact the patient by telephone and get a verbal assessment of the patient's condition. The phone conversation will then be documented in the patient's charts.

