11.2 Phase II

The primary objective of the phase II is to evaluate the efficacy of the combination in patients with FLT3-ITD mutated AML (n=20). The primary endpoint is the rate of CRc (CRc=CR/CRp/CRi) at any time during the first three cycles of therapy. The CRc will be monitored with a time window of 3 months, and toxicity will be monitored as DLT within 1 cycle of the treatment. CRc and toxicity will be monitored simultaneously using the Bayesian approach of Thall, Simon, Estey (1995, 1996) as extended by Thall and Sung (1998).

Of note, recent FDA approval of midostaurin in combination with 7+3 induction chemotherapy in newly diagnosed FLT3-mutant AML signifies that essentially all relapsed FLT3-mutated AML patient will likely have been exposed to at least one FLT3 targeting TKI. In this setting, the marrow response (CRc) rates with second generation FLT3 inhibitors such as crenolanib, gilteritinib and quizartinib have been reported to be lower than in prior FLT3 TKI naïve patients and are in the range of 20-25% (26, 48, 49) and Daiichi Sankyo unpublished communication).

Thus, the historical data suggested a CRc rate of 25% for this population with quizartinib alone and the target CRc with the quizartinib and venetoclax combination is 50%. The treatment will be considered worthy of further investigation if it elicits an increase in CRc to 50% or higher with acceptable toxicity. A >30% DLT rate is considered unacceptable. Given this, we will stop enrollment into this cohort if the observed patients' data suggest that:

- 1) $\Pr(\text{CRc}_E > \text{CRc}_H + 0.25 | \text{data}) < 0.025$ or
- 2) $\Pr(\text{TOX}_E > 0.30 | \text{data}) > 0.90$

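### Section 11.3 scores early drop-outs as failures even after a documented CRc, which contradicts the primary-endpoint rule in sections 8.8 and 11.2

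*Combined protocol and SAP*

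**What the plan says.** Three places in the combined protocol and SAP bear on how a patient is scored for the phase II primary endpoint.

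- Section 11.2 defines the endpoint as the rate of CRc (CR, CRp or CRi) "at any time during the first three cycles of therapy".
- Section 8.8 takes the best response over the first 3 cycles, "or at time off study, for those patients discontinuing treatment before the completion of 3 cycles of therapy". It defines best response as the best one measured up to that point, so an earlier CRc is kept.
- Section 11.3 includes everyone who received any dose and then says: "Patients who drop out of the study before completing all the cycles will be treated as" failures for the primary analysis. It makes no exception for a CRc already reached and does not say how many cycles are meant.

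Three other places affect the reading.

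- The phase 2 reporting paragraph of section 11.3 calls for "efficacy assessment by the end of cycle 3", which suggests that the three endpoint cycles are meant. The only planned total is up to 24 cycles (section 5.3.1).
- On leaving treatment versus leaving the study, section 9.1.1 says "Patients may also choose to withdraw from study treatment, but agree to remain in the study for follow-up procedures". Section 9.1.4 says that patients off treatment "will remain on study for follow-up evaluations" unless they withdraw consent, die or are lost.
- Section 8.0 describes the CRc rate as the "confirmed remission rate of all complete and incomplete CRs" but gives no confirmation rule.

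**The concern.** The same patient can be scored in opposite ways. Take a patient in CRc at the first scheduled marrow (section 7.2.6: "Bone marrow aspiration for differential and PCR for FLT3 on day 28" of cycle 1) who withdraws consent during cycle 2. Under 8.8 and 11.2 this is a success. Under 11.3 it is a failure. No section sets the order of precedence.

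Drop-out is also undefined. If it means stopping study treatment, a responder who stops to go to transplant within the window becomes a failure. If it means leaving follow-up, that patient is unaffected. Sections 9.1.1 and 9.1.4 separate the two ideas, but 8.8 uses time off study for patients who discontinue treatment.

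At stake is the sole phase II primary estimate, from 20 patients. Two analysts following different sections could report different CRc rates from identical data. The 11.3 rule can turn a success into a failure but never the reverse, so any error is downward.

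**Working it through.** **Side-by-side scoring**, taking the cycles in 11.3 to be the three endpoint cycles:

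| Patient | 8.8 / 11.2 | 11.3 |
|---|---|---|
| CRc in the window, completes cycle 3 | success | success |
| No CRc in the window, leaves early | failure | failure |
| CRc in the window, leaves the study before end of cycle 3 | success | failure |

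Only the third row conflicts. If up to 24 cycles were meant, many more responders would fall into it.

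**Inputs.** N = 20, historical CRc 25%, target CRc 50%, prior Beta(0.5, 1.5), stop accrual at 2 or fewer CRc in 10 or 4 or fewer in 15 (section 11.2, Table 4).

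**The plan's own figures reproduce.** The largest x with Pr(Beta(0.5+x, 1.5+n−x) > 0.50) < 0.025 is 2 at n = 10 (0.0149; x = 3 gives 0.064) and 4 at n = 15 (0.0210; x = 5 gives 0.066), as in Table 4. All 25 cells of Table 6 agree to within about 0.0001. For example, at true CRc 50% the stopping probability is 0.0836 at 10% toxicity (plan 0.0837) and 0.1605 at 30% toxicity (plan 0.1605). The widest 95% credible interval at N = 20 is 40.4%, consistent with the stated maximum of 41%. No stated figure is wrong. The problem is the scoring rule.

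**Effect on the final estimate.** With x scored responders in 20 the posterior is Beta(0.5+x, 21.5−x), with mean (0.5+x)/22. Each rescored responder lowers the mean by 1/22 = 4.5 percentage points.

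| Scored CRc | Mean | 95% credible interval |
|---|---|---|
| 10/20 | 10.5/22 = 47.7% | 27.7 to 68.1% |
| 9/20 (one rescored) | 9.5/22 = 43.2% | 23.7 to 63.8% |
| 8/20 (two rescored) | 8.5/22 = 38.6% | 19.9 to 59.3% |

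In this illustration one rescored patient moves the lower limit from above to below the 25% historical rate. The plan attaches no decision rule to that limit.

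**Conditional effect on futility stopping.** This applies only if the Table 4 counts used the 11.3 scoring, which the documents do not say. Let s be the share of responders rescored. The documents give no value, so the range is assumed. Scored CRc is p = 0.50 × (1 − s), and, with X10 the CRc count in the first 10 patients and X5 the count in the next 5,

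Pr(stop) = Pr(X10 ≤ 2) + Pr(X10 = 3) × Pr(X5 ≤ 1) + Pr(X10 = 4) × Pr(X5 = 0).

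At s = 0 this is 56/1024 + (120/1024)(6/32) + (210/1024)(1/32) = 0.0547 + 0.0220 + 0.0064 = 0.0831.

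| s | p | Futility stop |
|---|---|---|
| 0 | 50% | 8.3% |
| 10% | 45% | 15.4% |
| 20% | 40% | 25.9% |
| 40% | 30% | 55.7% |

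**The case against.** The strongest reply is that the 11.3 sentence is ordinary non-responder imputation. It follows the any-dose analysis set and keeps early leavers in the denominator, so what is missing is a qualifier limiting it to patients without a CRc. That is a plausible intent, but it is not what is written, and an analyst should not have to infer it once data are in hand.

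Second, drop-out may mean only leaving the study. Sections 9.1.1 and 9.1.4 support this, and it would spare responders who stop treatment for transplant. This narrows the conflict, perhaps to a few patients. It does not remove it, because a responder who withdraws consent or is lost before the end of cycle 3 is still scored both ways.

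Third, if a confirmed remission requires a second marrow, a patient who leaves in cycle 2 might be a non-responder under every section, since the next scheduled marrow is at the end of cycle 3. The cycle 1 example does depend on this. But the plan states no confirmation rule, 8.8 works from the best measured response, and 7.2.6 allows extra marrows, so a remission could be seen twice before the patient leaves.

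Fourth, 11.3 restricts its rule to the primary analysis, and section 11.2 appears to count responses for Table 4 as they occur. That point stands: the futility figures are conditional, and 40% rescoring would be extreme on the narrow reading of drop-out. The firm part of the size is the one- or two-patient shift, to be read against an interval about 40 points wide. The bias is conservative and cannot inflate CRc.

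**Conclusion.** The concern holds: 11.3 is wrong as written and should be corrected. It contradicts 8.8 and 11.2 for any patient who reaches CRc in the window and then drops out before the cycles are complete, and following it biases the primary estimate downward. Each affected responder costs 4.5 percentage points: from 47.7% to 43.2% for one and 38.6% for two, starting from an illustrative 10 in 20. The number affected cannot be derived from the documents. It depends on what drop-out means, on which cycles are meant and on an early-exit rate that is not given. The rise in futility stopping from 8.3% to between 15.4% and 55.7% assumes that 10% to 40% of responders are rescored and that Table 4 uses the same scoring. It should not be read as an expected effect.

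**What to change.** Replace the drop-out sentence in 11.3 with:

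> For the primary analysis, a patient who meets the section 8 criteria for CR, CRp or CRi at any time during the first three cycles, or by time off study if earlier (section 8.8), is a success regardless of later discontinuation for any reason. Treated patients with no documented CRc in that window, including those who leave unassessed, are failures.

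Add one clause stating that the Table 4 counts use the same scoring. Keep the any-dose analysis set and leave the section 8 definition of CRc unchanged. Whether confirmation requires a second assessment is a separate question that this wording does not settle.

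The cost is one sentence and one clause in section 11, with no extra data, visits or patients. The boundaries in Table 4 and the operating characteristics in Table 6 stand as published.

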8. Changes in drug dose and/or schedule must be discussed with and approved by the MDACC physician investigator, or their representative prior to initiation, and will be documented in the patient record.

7.2.11 For patients that remain on study with no significant toxicity for more than 6 months, subsequent evaluations during study may be modified after discussion with the PI. These include a decrease in frequency of bone marrow aspirations to every 6-12 months (or as clinically indicated) and other laboratory tests to once every cycle.

7.2.12 Pregnancy test (urine or serum) in females of childbearing potential every 3 months (\pm 2 weeks).

7.2.13 Patients will be followed for survival at MD Anderson Cancer Center (MDACC) every 3 to 6 months after the end of treatment visit for up to 5 years after completion of active treatment. If the patient is unable to return to MDACC the follow-up visits may be conducted via telephone.

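### DOR and EFS are censored at an undefined last follow-up, but after the 30-day visit only survival follow-up is specified, so a relapse nobody learns of can lengthen DOR

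*Combined protocol and SAP*

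**What the plan says.** **Censoring (11.3).** For DOR and EFS: "The observed DOR/EFS will be censored at the last follow-up if the patient is alive and no events observed". The next sentence uses the same term for survival: "The overall survival time is defined as the time duration from treatment start till death or last follow-up if the patient is alive". Neither sentence defines last follow-up or ties it to a disease assessment.

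**Events (11.3).** DOR runs from first documented CRc to recurrence, progression or death. EFS ends at "documented treatment failure, relapses from CRc, or death from any cause, whichever occurs first".

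**Assessment around the end of treatment (7.2.6, 9.1.4).** On-treatment marrows follow the treatment cycles. At discontinuation there is a physical examination, a CBC with differential and a limited chemistry profile. For marrow, 9.1.4 says: "A bone marrow aspiration may be recommended only if non-response or progressive disease cannot be unequivocally diagnosed from peripheral blood". A clinic visit for clinical evaluation and physical examination follows at 30 days. Section 9.1.4 also says that patients stay on study for follow-up evaluations, without giving their content or timing.

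**Later follow-up (7.2.13).** This phase can last 5 years, and its stated purpose is survival: "Patients will be followed for survival at MD Anderson Cancer Center (MDACC) every 3 to 6 months after the end of treatment visit". The section adds: "If the patient is unable to return to MDACC the follow-up visits may be conducted via telephone".

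**The concern.** Section 8.7 defines relapse after CR by blasts in blood, blasts in marrow or extramedullary disease. A contact made to establish survival, particularly by telephone, does not rule these out. If its date also serves as the censoring date for DOR and EFS, time in which nobody looked for relapse enters the Kaplan-Meier estimate as relapse-free time.

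The patients affected are responders who stop treatment without documented relapse, for example for toxicity or at their own request. Patients who stop for progression already have the event. Because death remains an event, an unlearned relapse is recorded late, at death, or not at all, and either outcome lengthens the estimate.

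The direction matters because the rationale (2.4) rests on durability: it puts single-agent responses at 14–17 weeks and expects the combination to hold them longer. The trial has one arm, so no concurrent control carries the same bias.

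**Working it through.** The plan gives no precision, power or event figure for DOR or EFS, so there is nothing to reproduce. The check has a textual part and an illustration of size.

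**1. Text.** Relapse can be recognised only from blood, marrow or extramedullary findings (8.7). The last protocol-specified occasions for a responder leaving treatment are the end-of-treatment CBC, a conditional marrow and the 30-day clinic visit (9.1.4). After that, 7.2.13 specifies survival only. Section 11.3 uses one undefined term for DOR, EFS and OS. The natural reading is therefore one date of last contact for all three.

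**2. Inputs for DOR (all assumptions, in weeks).**
- Time from CRc to relapse: exponential, median 16, inside the 14–17 weeks quoted in 2.4. λ = ln 2 / 16 = 0.0433 per week.
- A share p = 0.2, 0.3 or 0.4 of responders is liable to stop at a time uniform on weeks 4–24, independently of relapse risk.
- Median survival after relapse: 12 or 26.
- Data cut at 52 weeks.
- Share of off-treatment relapses learned of: 0, 50% or 80%.

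**3. Share actually stopping in remission.** p × (e^(−4λ) − e^(−24λ)) / (20λ) = p × (0.841 − 0.354) / 0.866 = 0.562p. This is 0.112 at p = 0.2 and 0.225 at p = 0.4, or 11–23%.

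**4. True relapse-free share at 26 weeks.** 2^(−26/16) = 0.324.

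**5. Result for DOR, simulated by Kaplan-Meier.**

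| Off-treatment relapses learned of | Median DOR (true 16.0) |
|---|---|
| none | about 16.7–18.1 |
| 50% | about 16.3–16.9 |
| 80% | about 16.1–16.3 |

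With none learned of, the 26-week relapse-free share is 35–40% against 32%, and the 52-week share is 13–20% against 10–11%. Censoring at the last disease assessment returns 16.0 weeks and 32%. It does so by construction, because stopping was simulated as independent of relapse.

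**6. Other settings, none learned of after the 30-day visit.** Take a true median of 17 weeks, stops 4–12 weeks after CRc, and data cuts at 52–156 weeks. The median becomes 18.1–19.1 if 20–30% are liable to stop, and up to 21.4 if 50% are. The direction is the same, and the size grows with the share stopping.

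**7. EFS.** Non-responders are 50–75% of patients at the planning CRc rates of 25–50% (11.2), and they dilute the effect. Assume response at week 4, and non-responder failure either at 12 weeks or exponential with median 8 weeks. Even with p = 0.4 and 26-week post-relapse survival, median EFS moves by 0–0.14 week. The 26-week EFS moves by about 1–3 points.

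**8. Precision.** Phase II expects 20 × 0.25 = 5 to 20 × 0.50 = 10 responders. With 10, the sample median of a 16-week exponential has a central 95% range of about 5–31 weeks. The standard error at 26 weeks is √(0.324 × 0.676 / 10) = 0.148, about 15 points.

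**The case against.** The strongest case on the other side is that this is an ambiguity and not an instruction. A reader might infer that the plan orders unassessed responders to be counted as relapse-free at each survival contact. No sentence says so: last follow-up is undefined, and a careful analyst could read it as last disease evaluation. Section 9.1.4 mentions further follow-up evaluations, the 30-day visit is clinical, and 7.2.13 makes attendance at the center the default, with telephone for patients who cannot return. Relapse may well be picked up at some of these contacts. This stands, and it is why the size is shown at 50% and 80% ascertainment as well as at zero. It does not remove the gap, because nothing requires relapse status to be sought or recorded.

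A reader might also infer that the same bias arises on treatment, since 7.2.11 lets marrows be spaced to every 6–12 months after 6 months. The documents do not support that. The same provision keeps marrows as clinically indicated and other laboratory tests once every cycle, and reappearance of blood blasts is itself relapse under 8.7. Late detection of a marrow relapse is also a different matter from the choice of censoring date.

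The bias is also small beside sampling error: 0.7–2.1 weeks and 3–8 points in the base illustration, against a range of roughly 5–31 weeks and a standard error of about 15 points with 10 responders. That is correct. But the error runs in one known direction, and with 5–10 responders one or two such patients can shape the tail of the curve.

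**Conclusion.** The point holds as a cheap improvement to a secondary analysis. On its natural reading, 11.3 lets time without disease assessment count as relapse-free time for responders who stop in remission. The direction is certain: DOR can only be lengthened. The size is modest, and it depends on how many responders stop in remission and how many later relapses are learned of, neither of which the documents give. Under the base assumptions the median moves from 16.0 weeks to at most about 18.1, and to 16.1–16.3 if 80% of relapses are learned of.

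Two stronger conclusions are not supported. EFS is not materially biased under the assumptions tried. The trial's main inference is not touched either: DOR and EFS are secondary, 11.3 plans no test of DOR against the 14–17 week figure, and the CRc endpoint and the stopping rules in 11.2 do not use these data.

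**What to change.** In 11.3, censor DOR and EFS at the last disease assessment adequate to exclude relapse (marrow, or CBC with differential), and keep date of last contact for OS only. In 7.2.13, record at each existing survival contact whether and when relapse was diagnosed and whether new anti-leukemia therapy was started, from the patient or outside records.

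The cost is a sentence in the analysis plan and two items on a contact that already takes place, with no added visits or procedures. The price is shorter DOR and EFS follow-up and slightly wider intervals. Censoring at last assessment still assumes that stopping is unrelated to relapse risk. The recorded relapse date reduces reliance on that assumption but does not remove it.
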